6.7. Appendix 7 Intervention Compliance

Not applicable.

6.8. Appendix 8 Adverse Events of Special Interest

The following adverse events of special interest will be used for selexipag. These are based on the important identified and potential risks in the latest Risk Management Plan and on-going discussion with Pharmacovigilance Risk Assessment Committee.

| AE Special Interest Category |
|--|
| Anaemia |
| Bleeding events |
| Gastrointestinal disturbances denoting intestinal intussusception (manifested as ileus or obstruction) |
| Hyperthyroidism |
| Hypotension |
| Light-dependent non-melanoma skin malignancies |
| Major adverse cardiovascular events (MACE) |
| Medication errors |
| Ophthalmological effects associated to retinal vascular system |
| Pregnancy |
| Pulmonary venoocclusive disease associated with pulmonary oedema |
| Renal function impairment / acute renal failure |
| Prostacyclin associated reactions* |

*Prostacyclin associated reactions will be summarized separately from other AESIs

Adverse events of special interest are defined in the aesi220.xlsx file available in SPACE.

6.9. Appendix 9 Medications of Special Interest

Anticoagulants and antithrombotic are selected based on the ATC code available in the Standard Definition Group (SDG) Excel file available in SPACE (SDG_B3C3_March1_2020_126.xlsx). The SDG file contains all possible antithrombotic medications in line with the WHO drug dictionary version (March 2020) used in A302 and A303. It will be used to identify the anti-thrombotic medications given during these studies.

6.10. Appendix 10 Titration and maintenance periods

In the A302 CSR SAP, titration and maintenance periods are defined as follows:

- The study intervention Titration Period starts at date of first intake of study intervention and ends at Day 86 (or earlier, if selexipag is discontinued before). Study Day 86 has been chosen according to the study protocol-specified maximum duration of the Titration Period including a 3 days tolerance.
- The study intervention Maintenance Period starts at Day 87 and ends at the date of last intake of study intervention.

Note: The definition of titration/maintenance period in the A303 protocol is not clear, in fact in Section 3.10.2.10 it seems that Week 16 is included in the titration period. For OLS and STS (A302+A303), titration period should be considered to end at Week 12 as defined in the summary of clinical safety (SCS) of the first NDA/MAA submission in 2014. In the A302 protocol, the first dose was to be given in the afternoon at study day 1 with an exposure duration of 0.5 day. Thus, the duration of titration period, for participants who did not prematurely stop the study intervention during the titration period, was considered as 86.5 days in the SCS for the first NDA/MAA. However, for the onset of adverse events only the date (without time) was collected. In addition, data of study drug log in CRF cannot distinguish whether a patient received afternoon dose only or both morning and afternoon doses. Therefore, the SCS for the sNDA/MAA submission in 2020, RMPs and newly completed selexipag studies were summarized without using such half-day convention and the titration period ended at day 86.

Participants who entered A303 might have experienced a titration period in A302 and another titration period in A303. For STS (A302+A303), only the first titration period with Selexipag is taken, i.e., for participants who received Selexipag already in A302, the titration period in A302 is taken; for participants who received Selexipag only in A303, the titration period in A303 is taken.

For OLS, for participants who received Selexipag in A302 and A303, the titration period in A303 is taken; for participants who received Selexipag only in A303, the titration period in A303 is taken. In case a participant received Selexipag in A302 and A303 but without titration in A303, the entire A303 period is considered as maintenance, hence no titration period in OLS.

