1.4.8 Statistical hypotheses and sample size

No statistical hypothesis is considered for this OL study.

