1.2. Study Design

This is a multicenter, open-label study to assess long-term safety and tolerability of selexipag in participants with PAH.

Participants (males or females aged 18 years or older) from the study A302 were enrolled between 07 July 2010 and 02 September 2014 in this A303 study. This participant population consists of 3 cohorts:

- Cohort 1: Participants who completed the study A302 including the Treatment Extension Period (TEP) as scheduled per protocol (i.e., treated until unblinding of the study) without morbidity event.
- Cohort 2: Participants who experienced a morbidity event (had to be confirmed by the Critical Event Committee [CEC]) during the study A302.
- Cohort 3: Participants who experienced a worsening of PAH during the TEP of A302 and for whom a written approval to enter study A303 had been obtained from the sponsor.

The study is conducted in 155 centers in 39 countries.

Visit 1 in the A303 study should correspond to the last visit in study A302. If this was not possible, Visit 1 had to be performed not later than 2 weeks (14 days) after the last visit in study A302.

Participants of Cohort 2 and Cohort 3 were enrolled in the A303 study without knowledge of their previous treatment to preserve the integrity of the double-blind A302 study. All these participants entered the titration period of A303, i.e., they started selexipag at the lowest dose (200 µg bid).

Participants of Cohort 1 were eligible to enter the A303 study with knowledge of their previous study intervention allocation (selexipag or placebo). Participants who were receiving selexipag in A302 directly entered the maintenance period in A303 at the same dose of selexipag they were receiving at the end of the A302 TEP, except participants who were with treatment interruption ≥ 3 days between studies would enter the titration period of A303. Participants who were receiving placebo in A302 entered first the titration period of A303, i.e., started selexipag at the lowest dose (200 µg bid). Participants with a treatment interruption of at least 3 days between both studies (irrespective of whether randomized to selexipag or placebo) also entered the titration period of A303.

Treatment in the titration period of A303 was started at a selexipag dose of 200 µg bid with subsequent up-titration by 200 µg bid increments to achieve the individual MTD (maximum

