5.1.3.2. For Selexipag treated Set

Study Day 1 (or Day 1) refers to the start date of the first selexipag administration in either A302 or A303 (whichever is earlier), as defined in Section 4. If the start date is missing, the date of Visit 1 of A302 or A303 (whichever is earlier) in CRF will be used.

EOT refers to the date of the last selexipag administration in A302 or A303, whichever is later.

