5.5.1.1. Definition of IMTD

The IMTD (mcg b.i.d.) is defined by the following rules regardless of length of the titration period:

- Participants who entered the study defined maintenance period (=who completed the study titration period, Section 6.10):
 - IMTD is defined as the last b.i.d. dose at the end of titration period
- Participants who did not enter the study defined maintenance period (=who withdrew from the study during the study titration period, Section 6.10):
 - IMTD is defined as the highest b.i.d. dose without dose reduction afterward.
 - If no up-titration attempted, IMTD is defined as zero.

The IMTD (mcg b.i.d.) categories are defined for both STS (A302+A303) and OLS as

- 0
- 200-400
- 600-1000
- 1200-1600

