5.5.2.3. Treatment-Emergent prostacyclin associated reactions

Definition: The detailed definition of TE prostacyclin associated reactions (i.e., selected TE-AEs) is given as one of the AESI categories in Section 6.8. In addition, TE-AEs during each period are defined as:

- TE-AEs in the titration period (Section 6.10): Any prostacyclin associated reaction that occurred at or after the initial administration of study intervention through Day 86, or EOT plus 3 days for participants who discontinued study intervention in the titration period.

- TE-AEs in the maintenance period (Section 6.10): Any prostacyclin associated reaction that occurred at or after Day 87 through EOT plus 3 days. Participants who discontinued during the titration period are excluded from the denominator.

Population: All participants included in the STS (A302+A303) and OLS

Study Intervention: Selexipag

Outcome measures: Binary variables, occurrence of TE-prostacyclin associated reactions (Yes/No)

Summary method(s) for outcome measure:

- The same analysis applied for TE-AESI in “Summary method(s) for outcome measure” paragraph (Section 5.5.2.2).
- All TE-prostacyclin associated reactions will also be reported for subgroups by PAH medication at baseline - group 1 (defined in Section 5.6.8)
- All TE-prostacyclin associated reactions will also be reported separately for the titration period and the maintenance period. Participants who entered A303 might have experienced a titration period in A302 and another titration period in A303; in this case the rule in Section 6.10 is followed.
- Total TE subject-years will also reported separately for the titration period and the maintenance period (Section 5.5.1.2).

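### In the pooled Selexipag-treated Set, A303 re-titration after Day 86 is counted as maintenance for prostacyclin associated reactions, while the OLS columns of the same tables call it titration

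*SAP*

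**What the plan says.** **Who titrates twice.** SAP 1.2 says of Cohorts 2 and 3, who entered A303 without knowledge of their A302 arm: "All these participants entered the titration period of A303". The protocol synopsis (Study Periods) confirms that this applies whatever the A302 arm. Cohort 1 participants from the selexipag arm continued at their existing dose, unless treatment had been interrupted for 3 days or more between the studies.

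**STS clock.** Under SAP 5.1.3.2, Day 1 is the first selexipag dose in either study and end of treatment (EOT) is the last dose in either.

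**STS period rule.** SAP 6.10 states that "only the first titration period with Selexipag is taken", and spells out that "for participants who received Selexipag already in A302, the titration period in A302 is taken". The window is: "The study intervention Maintenance Period starts at Day 87 and ends at the date of last intake of study intervention". SAP 5.5.1.2 gives 86 days of titration exposure to everyone who did not stop before Day 86 and books the rest, to EOT plus 3 days, as maintenance. SAP 5.5.2.3 defines maintenance events as "Any prostacyclin associated reaction that occurred at or after Day 87 through EOT plus 3 days", and refers participants with two titrations back to 6.10.

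**OLS period rule.** The same appendix takes the A303 titration for ex-selexipag participants. All of A303 is maintenance only where there was no A303 titration. SAP 4 and 5.5 put the OLS and STS columns side by side.

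**Dose label.** For participants who reach maintenance, SAP 5.5.1.1 says "IMTD is defined as the last b.i.d. dose at the end of titration period". SAP 5.5.1 tabulates treatment duration by category of that dose (IMTD).

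**The concern.** The split between titration and maintenance shows whether prostacyclin associated reactions persist once dosing has settled. In the STS columns, part of a second up-titration is filed under maintenance. Two adjacent columns can then describe the same reaction in the same participant differently. SAP 1 says the completed summary can be used to update the submission tables, so the STS maintenance figure may be read as a long-term tolerability estimate. The participants affected are mainly those who worsened in A302.

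**Working it through.** **1. Set sizes (SAP 4).** 330 + 379 = 709 (OLS) and 574 + 379 = 953 (STS). Both reproduce. The plan states no maintenance rate, so there is no other figure to reproduce.

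**2. One participant.** Take the median A302 selexipag exposure in SAP 1, 18.8 months × 30.4 = 572 days. Assume no gap and 1,095 days in A303.
- Treatment-emergent exposure: 572 + 1,095 + 3 = 1,670 days.
- STS as written: 86 titration days and 1,670 − 86 = 1,584 maintenance days.
- The A303 re-titration window is STS Days 573 to 658, wholly inside maintenance: 86 / 1,584 = 5.4%.
- Split out: 86 titration, 86 re-titration and 1,498 maintenance days.

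**3. An early entrant.** If A303 starts on STS Day 55, A303 Day 32 is STS Day 86. The first 32 days of re-titration already lie in the STS titration window, and the other 54 fall in maintenance. Only days after STS Day 86 are misfiled.

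**4. Effect on the annualised rate.** Let k be the number re-titrating, N the column size, y the mean exposure in years and RR the reaction rate in re-titration divided by that in other maintenance time.
- Re-titration subject-years = k × 86 / 365.25
- Maintenance subject-years M = N × (365.25y + 3 − 86) / 365.25
- Relative excess = (re-titration subject-years / M) × (RR − 1)

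Assumptions: k = 82 (about a quarter of 330), y = 2 to 4, RR = 2, 5 or 10. All re-titration days are taken to fall after STS Day 86, early stoppers are ignored, and the underlying maintenance rate is the same for everyone. Re-titration subject-years = 82 × 86 / 365.25 = 19.3.

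| Column | y | M | Share | RR 2 | RR 5 | RR 10 |
|---|---|---|---|---|---|---|
| Selexipag in A302 (574) | 2 | 1,018 | 1.90% | +1.9% | +7.6% | +17.1% |
| Selexipag in A302 (574) | 4 | 2,166 | 0.89% | +0.9% | +3.6% | +8.0% |
| All (953) | 2 | 1,689 | 1.14% | +1.1% | +4.6% | +10.3% |
| All (953) | 4 | 3,595 | 0.54% | +0.5% | +2.1% | +4.8% |

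At RR = 1 every entry is zero. The excess is proportional to k: with k = 33, 'All' runs from +0.2% (RR 2, y = 4) to +4.1% (RR 10, y = 2).

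**5. Effect on the percentage with a reaction.** Participants with other maintenance time are in the denominator anyway, so counting re-titration reactions can add to the numerator but not take away. The ceiling at k = 82 is 82 / 953 = 8.6 points in 'All' and 82 / 574 = 14.3 points in 'Selexipag in A302'. Participants who stop during titration leave the denominator, so the actual ceilings are slightly higher. They would be reached only if every re-titrator reacted in re-titration and never otherwise in maintenance.

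**The case against.** The strongest reply is that this is a declared convention. SAP 5.5.2.3 and 6.10 recognise the two-titration case and set a rule for each analysis set. STS runs from first-ever selexipag, matches earlier submissions, and sits beside OLS columns that do use the A303 titration. That stands as far as disclosure goes. It does not repair the STS columns, because OLS leaves out A302 maintenance time. SAP 6.10 justifies the 86-day cut-off but gives no reason for treating re-titration as maintenance.

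Second, SAP maintenance is a calendar window and not a titration-free state. Protocol 1.4.5 and 3.4.1 provide for up-titration during maintenance and for re-titration after later interruptions, and those episodes are counted as maintenance too. That is correct, and it limits how clean any split can be.

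Third, the size could be small. Re-titrating participants have taken the drug before, and protocol 1.3.2.1 reports Phase 1 data suggesting better tolerability with repeated dosing. The scheduled steps in protocol 3.3.3 end at Week 8, so a raised rate over all 86 days is generous. If it held for only 56 days, the ranges above would shrink by 56/86, to about 0.6% to 11% in 'Selexipag in A302' and 0.3% to 7% in 'All'.

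A reader might also infer that A303 exposure is tabulated under a wrong dose. The documents do not support that. IMTD is a fixed label per participant, used only to describe dose and exposure, and the A303 dose may fall in the same broad category.

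**Conclusion.** The classification point holds on the SAP text. For ex-selexipag participants who re-titrated in A303, the part after STS Day 86 is booked as maintenance in events and in subject-years. It is a narrow point: the split applies to one of the 13 special-interest categories in SAP 6.8. Overall reaction totals and the three protocol endpoints (protocol 3.8.2) do not change, and no test is affected, since "No statistical hypothesis is considered for this OL study".

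Upward movement is assured only for the participant percentage, with the denominator held. For the annualised rate it needs RR above 1. The rationale for gradual titration in protocol 1.4.5 makes that plausible, but no figure shows it. The size is unknown: about 1% to 17% in 'Selexipag in A302' and 0.5% to 10% in 'All' under the assumptions above.

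A reader might infer a large distortion, or that all 330 ex-selexipag participants are affected. Neither is supported. Uninterrupted Cohort 1 participants did not re-titrate, and the larger figures need many re-titrators together with a high rate ratio, neither of which the documents give.

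**What to change.** In SAP 6.10, 5.5.1.2 and 5.5.2.3:

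- Report the number of STS participants who re-titrated in A303.
- Add an STS row set, or a sensitivity analysis, with a re-titration category. For these participants it covers A303 Days 1 to 86, limited to days after STS Day 86 and ending no later than EOT plus 3 days. The limit prevents days from being assigned twice when A303 starts before STS Day 87.
- Remove those days and events from maintenance. Remove a participant from the maintenance denominator only where no maintenance time remains.
- Keep the convention of the 2014 and 2020 submissions alongside, for continuity.
- State that re-titration after later interruptions stays in maintenance.

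Optionally, footnote the STS exposure-by-IMTD table with the number of re-titrators whose category changed in A303. Do not split one participant's duration across categories in the main table.

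The cost is one extra row set and modest programming. The A303 titration status, dates and IMTD are already needed for OLS. No data collection or clinical procedure changes.
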